5.2. SUBJECT SELECTION

5.2.1. Inclusion Criteria

Subjects are eligible to be included in the study only if all of the following criteria apply:

- 1. Subject must be 18 to 65 years of age inclusive, at the time of signing the informed consent.
- 2. Evidence of asthma as documented by either:
 - Airway reversibility (FEV1≥12% and 200 ml) demonstrated at Visit 1 (screening), or Visit 2 (Week 0) OR documented in the previous 12 months OR
 - Airway hyper-responsiveness (methacholine: PC20 of <8mg/mL or histamine: PD20 of <7.8 µmol; mannitol: decrease in FEV1 as per the labelled product instructions) documented in the 12 months prior to Visit 2 (Week 0) OR
 - Airflow variability in clinic FEV1 ≥20% between two consecutive clinic visits documented in the 12 months prior to Visit 2 (FEV1 recorded during an exacerbation should not be considered for this criteria) OR
 - Airflow variability as indicated by >20% diurnal variability in peak flow observed on 3 or more days during the optimisation period

3. Participants with Eosinophilic asthma: prior documentation of eosinophilic asthma or high likelihood of eosinophilic asthma as

FEV1: Persistent airflow obstruction as indicated by:

For participants ≥ 18 years of age at Visit 1 (screening), or Visit 2 (Week 0), a prebronchodilator FEV1 <80% predicted

For predicted FEV1 values NHANES III values will be used and adjustments to these values will be made for race [Hankinson, 1999].

4. Eosinophilic Phenotype: Airway inflammation characterized as eosinophilic in nature as indicated by one of the following characteristics:

a. An elevated peripheral blood eosinophil level of \geq 300 cells/µL that is related to asthma within the previous 12 months prior to Visit 2 (Week 0) OR

b. Peripheral baseline eosinophil level ≥150 cells/µL between Visit 1 (screening) and Visit 2 (Week 0) that is related to asthma.

- 5. Patients eligible for mepolizumab treatment as per independent clinical judgment of treating physician in alignment with local prescribing information.
- 6. Inhaled Corticosteroids: requirement for regular treatment with high dose inhaled corticosteroid in the 6 months prior to Visit 1 (screening).

For 18 years of age and older:

• ICS dose must be ≥880 mcg/day fluticasone propionate (FP) (ex-actuator) or equivalent daily.

 Controller Medication: Current treatment with an additional controller medication for at least 3 months OR having used and failed an additional controller medication for at least 3 successive months during the prior 12 months [e.g., long-acting beta2-agonist (LABA), leukotriene receptor antagonist (LTRA), or theophylline].

Sex

8. Male or eligible female

Contraceptive use by women should be consistent with local regulations regarding the methods of contraception for those participating in clinical studies. Female Participants: A female participant is eligible to participate if she is not pregnant or breastfeeding, and at least one of the following conditions applies:

- Is not a woman of childbearing potential (WOCBP)
- OR

• Is a WOCBP and using a contraceptive method that is highly effective, with a failure rate of <1%, as described in Appendix 4 of the protocol during the intervention period and for at least 16 weeks after the last dose of study intervention. The investigator should evaluate the effectiveness of the contraceptive method in relationship to the first dose of study intervention.

- A WOCBP must have a negative highly sensitive (Appendix 2 of the protocol) pregnancy test (serum) within 8 weeks before the first dose of study intervention.
- Additional requirements for pregnancy testing during and after study intervention are located in Appendix 2 of the protocol.
- The investigator is responsible for review of medical history, menstrual history, and recent sexual activity to decrease the risk for inclusion of a woman with an early undetected pregnancy

Informed Consent

9. Capable of giving signed informed consent as described in Appendix 1 of the protocol which includes compliance with the requirements and restrictions listed in the informed consent form (ICF) and in this protocol.

5.2.2. Exclusion Criteria

Subjects are excluded from the study if any of the following criteria apply:

Medical Conditions

- 1. Concurrent Respiratory Disease: Presence of a clinically important lung condition other than asthma. This includes but is not limited to current infection, bronchiectasis, pulmonary fibrosis, bronchopulmonary aspergillosis, or diagnoses of emphysema or chronic bronchitis (chronic obstructive pulmonary disease other than asthma) or a history of lung cancer.
- 2. Malignancy: A current malignancy or previous history of cancer in remission for less than 12 months prior screening (Participants who had localized carcinoma (i.e. basal or squamous cell) of the skin which was resected for cure will not be excluded).
- 3. Liver Disease: Unstable liver disease (as defined by the presence of ascites, encephalopathy, coagulopathy, hypoalbuminemia, oesophageal or gastric varices or persistent jaundice), cirrhosis,

and known biliary abnormalities (with the exception of Gilbert's syndrome or asymptomatic gallstones).

- 4. Cardiovascular: Participants who have severe or clinically significant cardiovascular disease uncontrolled with standard treatment. Including but not limited to:
 - Known ejection fraction of <30% OR
 - severe heart failure meeting New York Heart Association Class IV (Appendix 5 of the protocol) OR
 - hospitalized in the 12 months prior to Visit 1 for severe heart failure meeting New York Heart Association Class III (Appendix 5 of the protocol) OR
 - angina diagnosed less than 3 months prior to Visit 1 (screening) or at Visit 1
- 5. Other Concurrent Medical Conditions: Participants who have known, pre-existing, clinically significant endocrine, autoimmune, metabolic, neurological, renal, gastrointestinal, hepatic, haematological or any other system abnormalities that are uncontrolled with standard treatment.
- 6. Eosinophilic Diseases: Participants with other conditions that could lead to elevated eosinophils such as Hypereosinophilic Syndromes, including Churg-Strauss Syndrome, or Eosinophilic Esophaghitis.
- 7. Participants with a known, pre-existing parasitic infestation within 6 months prior to Visit 1 (screening) are also to be excluded.

Prior/Concomitant Therapy

- 8. Omalizumab Use: Participants who have received omalizumab [Xolair] within 130 days of Visit 1 (screening)
- 9. Other Monoclonal Antibodies: Participants who have received any monoclonal antibody (other than Xolair) to treat inflammatory disease within 5 half-lives of Visit 1 (screening).
- Investigational Medications: Participants who have received treatment with an investigational drug within the past 30 days or five terminal phase half-lives of the drug whichever is longer, prior to Visit 1 (this also includes investigational formulations of marketed products).

Prior/Concurrent Clinical Study Experience

11. Participants who have previously participated in any study of mepolizumab and received Investigational Product (including placebo).

Diagnostic assessments

12. ECG: ECG assessment QTcF > 450msec or QTcF > 480 msec for participants with Bundle Branch Block.

- Participants are excluded if an abnormal ECG finding from the 12-lead ECG conducted at Screening (Visit 1) is considered to be clinically significant and would impact the participant's participation during the study, based on the evaluation of the Investigator.
- 13. Immunodeficiency: A known immunodeficiency (e.g. human immunodeficiency virus HIV), other than that explained by the use of corticosteroids taken as therapy for asthma.

COVID-19 Related Exclusion

14. Participants that have a current active COVID-19 infection, either laboratory confirmed or according to the investigator's medical judgement.

Note: Participants who have confirmed or suspected COVID-19 infection may be rescreened 4 weeks or more after the resolution of the COVID-19 infection and only after written approval from the study Medical Monitor.

15. Participants known to be in contact with active COVID-19 positive individuals within the past 14 days.

Note: Participants may be re-screened 14 days or more following the contact, during which the participant should remain symptom free, and only after written approval from the study Medical Monitor.

Other Exclusions

- 16. Smoking history: Current smokers or former smokers with a smoking history of ≥10 pack years. A former smoker is defined as a participant who quit smoking at least 6 months prior to Visit 1 (screening)
- 17. Hypersensitivity: Participants with a known allergy or intolerance to a monoclonal antibody or biologic.
- 18. Pregnancy: Participants who are pregnant or breastfeeding. Patients should not be enrolled if they plan to become pregnant during the time of study participation.
- 19. Alcohol/Substance Abuse: A history (or suspected history) of alcohol misuse or substance abuse within 2 years prior to Visit 1 (screening).
- 20. Adherence: Participants who have known evidence of lack of adherence to controller medications and/or ability to follow physician's recommendations.

Re-screening of participants will be allowed only upon approval by the medical monitor.

5.3. DETERMINATION OF SAMPLE SIZE

The primary objective of the study is to evaluate the safety and tolerability of mepolizumab over 24 weeks of treatment. The primary endpoint is incidence of AEs, SAEs and AESIs. Sample size is determined based on the calculation of the probability of observing an AE. Table 3 provides the probabilities of observing various numbers of AEs based on a series of theoretical risks of an event occurring in a given patient in a study of 24 weeks' duration, given a sample size of 100. For example, for a theoretical risk of an AE of 2/100 (true proportion value of 0.02) in this 24-week study, we would have a greater than 86% chance of observing at least one subject having the AE.

Table Probabilities of observing a given number of subjects experiencing an adverse events or more (k) for given anticipated risks for a sample size of 100 patients.

| Theoretical Risk of an Event* | | | | | | |
|-------------------------------|---------|---------|----------|----------|-----------|--|
| No of AEs | 5% risk | 3% risk | 2% risk | 1% risk | 0.5% risk | |
| K | 0.05 | 0.03 | 0.02 | 0.01 | 0.005 | |
| 1 | 0.9941 | 0.9524 | 0.8673 | 0.6340 | 0.3942 | |
| 2 | 0.9629 | 0.8053 | 0.5967 | 0.2642 | 0.0898 | |
| 3 | 0.8817 | 0.5802 | 0.3233 | 0.0794 | 0.0141 | |
| 4 | 0.7422 | 0.3528 | 0.1411 | 0.0184 | 0.0017 | |
| 5 | 0.5640 | 0.1821 | 0.0508 | 0.0034 | 0.0002 | |
| 6 | 0.3840 | 0.0808 | 0.0155 | 0.0005 | ≤ 0.0001 | |
| 7 | 0.2340 | 0.0312 | 0.0041 | ≤ 0.0001 | ≤ 0.0001 | |
| 8 | 0.1279 | 0.0106 | 0.0009 | ≤ 0.0001 | ≤ 0.0001 | |
| 9 | 0.0631 | 0.0032 | 0.0002 | ≤ 0.0001 | ≤ 0.0001 | |
| 10 | 0.0282 | 0.0009 | ≤ 0.0001 | ≤ 0.0001 | ≤ 0.0001 | |

*Theoretical risk of an event occurring in a given patient in a study of 24 weeks' duration.

Assuming a 35% screen failure rate approximately 154 participants will be required to be screened in order for 100 participants to be enrolled onto the study treatment.

5.4. TREATMENT ASSIGNEMENT AND MASKING

This is an open-label study. All subjects enrolled in the induction phase will receive the study drug (100 mg mepolizumab SC every 4 weeks).

6. ANALYSIS POPULATIONS

For the purpose of analysis, the following population are defined:

6.1. ALL ENROLLED POPULATION

All participants enrolled and for whom a participant number exists on the study database. This population will be used for summarizing reasons for screen and run-in failures.

6.2. SAFETY POPULATION

All participants who take at least 1 dose of study intervention. This population will be used for all safety, efficacy and health outcomes.

7. GENERAL ASPECTS FOR STATISTICAL ANALYSIS

7.1. GENERAL CONSIDERATIONS

Continuous data will be summarized using the number of subjects (n), arithmetic mean (mean), standard deviation (SD), median, minimum value (min), and maximum value (max) values unless otherwise specified. Categorical variables will be summarized using the frequency counts (n) and percentages (%) for each possible value. Where log-transformed data are used, the summary statistics will include geometric mean and geometric standard deviation (SD). Only data from protocol scheduled visits will be included in the summary tables. Data from unscheduled visits will not be included in the summary tables.

7.2. KEY DEFINITIONS

7.2.1. Study/Onset Day

The study/onset day will be defined as the number of days since the first dose of study drug, which is assigned as Day 1 for analysis purposes. Study/onset day is calculated using the formula below:

| Assessment Date Relative to First Dose of Study Drug | Study Day Calculation |
|--|---|
| Assessment/Event date < Date of first dose | Date of assessment - Date of first dose of study drug |
| Assessment/Event date ≥ Date of first dose | (Date of assessment – Date of first dose of study drug)+1 |

7.2.2. Baseline, Change from Baseline, Relative Change from Baseline and Ratio to Baseline

Baseline is defined as the value recorded at Visit 1 pre-dose assessment. For data collected via eDiary device, the baseline is defined as the average of 4-weekly data collected in the run-in period.

On Visit 2, where time of assessment is collected/available, this should be used to determine if the assessment was performed prior to the administration of the study drug. Where time of assessment is not collected/available it will be assumed that all assessments on Visit 2 occurred prior to the administration of the study drug.

Change from baseline, relative change from baseline and ratio to baseline are calculated as follows:

- Change from baseline = (Post-baseline value Baseline value)
- Relative change from baseline (%) = (Post-baseline value Baseline value)/(Baseline value)*100
- Ratio to baseline = Post-baseline value /Baseline value

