1.3. Schedule of Activities (SoA)

Table 1 Time and Events Table

Procedure	Pre- Screen	Screenin g	Treatment Period (visit window is ± 7days)			IP Discontinu ation visit	End of study visit	Notes			
Visit		1	2	3	4	5	6	7		8	
Week		-2 to -1	0	4	8	12	16	20	4 weeks post last dose ± 7 days	24 or Early Withd rawal	
Written Informed Consent	X	X									 Pre-screen visit can occur on the same day as the Visit 1 but must be completed prior to starting Visit 1 (screening) procedures. Visit 2 (Week 0) must occur at least one week following Visit 1 (screening) Visit 2 (Week 0) will be considered Baseline
Demography		X								:	
Medical History		X									
Asthma and Exacerbation History (including triggers)		Х									
Asthma Therapy History		X									Therapy history to include a detailed review of prior monoclonal antibodies received for treatment of asthma, including prior investigational anti-IL5 or anti-IL13 preparations.

Procedure	Pre- Screen	Screenin g		Treatment Period (visit window is ± 7days)			IP Discontinu ation visit	End of study visit	Notes		
Visit		1	2	3	4	5	6	7		8	
Week		-2 to -1	0	4	8	12	16	20	4 weeks post last dose ± 7 days	24 or Early Withd rawal	
Oral Corticosteroid Therapy History		X									
Smoking History		X									
Cardiovascular History/risk factors		X									
Parasitic Screening		X									
Inclusion/Exclusion Criteria		х	х								Study inclusion/exclusion criteria should be reviewed at the beginning of visit 2(Week 0). The review should include the results of any lab/safety assessments conducted at Visit 1 (screening).
Treatment Period Criteria			x								
Efficacy Assessments						_		_			
Exacerbation review			х	X	X	х	х	х	X	Х	Number of clinically significant exacerbations (including exacerbations requiring hospitalization, Emergency Department) visits will be evaluated
Spirometry including FEV ₁ , FVC		Х	х		Х		Х		X	Х	

Procedure	Pre- Screen	Screenin g	Treatment l		7days)				IP Discontinu	End of study	Notes
									ation visit	visit	
Visit		1	2	3	4	5	6	7		8	
Week		-2 to -1	0	4	8	12	16	20	4 weeks post last dose ± 7 days	24 or Early Withd rawal	
Maximum Post Bronchodilator Procedure		х	x						х	X	Maximum Post Bronchodilator Procedure is required to complete reversibility testing. If participant does not reverse ≥12% in FEV₁ at Visit 1 (screening), the procedure may be repeated at Visit 2 (Week 0).
OCS dose adjustment review (where applicable)		Х		х	Х	Х	Х	Х			OCS dose adjustment should be reviewed at scheduled in-clinic Visits

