For All other criteria:

- Repeat liver chemistries (include ALT, AST, alkaline phosphatase, bilirubin and INR) and perform liver event follow up assessments within 24-72 hrs
- Monitor participants weekly until liver chemistries resolve, stabilize or return to within baseline i.e. Visit 3

bilirubin≥2xULN

- Obtain complete blood count with differential to assess eosinophilia
- Record the appearance or worsening of clinical symptoms of liver injury, or hypersensitivity, on the AE report form
- Record use of concomitant medications on the concomitant medications report form including acetaminophen, herbal remedies, other over the counter medications.
- Record alcohol use on the liver event alcohol intake case report form (CRF) page

For bilirubin or INR criteria:

- Anti-nuclear antibody, anti-smooth muscle antibody, Type 1 anti-liver kidney microsomal antibodies, and quantitative total immunoglobulin G (IgG) or gamma globulins.
- Serum acetaminophen adduct high performance liquid chromatography (HPLC) assay (quantifies potential acetaminophen contribution to liver injury in participants with definite or likely acetaminophen use in the preceding week [James, 2009]).
- Liver imaging (ultrasound, magnetic resonance, or computerised tomography) and /or liver biopsy to evaluate liver disease; complete Liver Imaging and/or Liver Biopsy CRF forms.
- 1. Serum bilirubin fractionation should be performed if testing is available. If serum bilirubin fractionation is not immediately available, discontinue study intervention for that participant if ALT ≥ 3xULN and bilirubin ≥ 2xULN. Additionally, if serum bilirubin fractionation testing is unavailable, record presence of detectable urinary bilirubin on dipstick, indicating direct bilirubin elevations and suggesting liver injury.

- 2. All events of ALT \geq 3xULN and bilirubin \geq 2xULN (>35% direct bilirubin) or ALT \geq 3xULN and INR>1.5 which may indicate severe liver injury (possible 'Hy's Law'), must be reported as an SAE (excluding studies of hepatic impairment or cirrhosis); the threshold value stated will not apply to participants receiving anticoagulants
- 3. New or worsening symptoms believed to be related to liver injury (such as fatigue, nausea, vomiting, right upper quadrant pain or tenderness, or jaundice) or believed to be related to hypersensitivity (such as fever, rash or eosinophilia)

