2. INTRODUCTION

The purpose of this document is to provide a description of the statistical methods and procedures to be implemented for the analysis of data from GSK 209682 study. This document is based on the protocol version Amendment 4, dated 23 August 2022. This Statistical Analysis Plan (SAP) has been developed prior to database lock for final analysis. Any changes from the planned analysis as described in the protocol GSK 209682 and its amendments (as applicable) are detailed here, and any differences described here supersede the analysis presented in the protocol. Any additional analyses which are conducted to supplement the planned analyses and any deviations from the planned analyses described in this SAP will be documented in the Clinical Study Report (CSR).

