7.2.6. Asthma Exacerbations

For the analysis of exacerbations, the exacerbation follow-up time is defined as:

- For subjects completed the study: Date of Week 24 visit Date of Baseline (Week 0) visit +1
- For subjects with early withdrawals: Date of Withdrawal Date of Baseline (Week 0) visit + 1

The on-treatment assessment period for exacerbations is calculated from date of Baseline (Week 0) visit to date of Week 24 visit or early withdrawal (inclusive).

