9.2. DEMOGRAPHIC AND BASELINE CHARACTERISTICS

Subjects' demographics and baseline characteristics will be summarized for the safety population.

Continuous variables (e.g., age and weight) will be summarized using descriptive statistics (n, mean, standard deviation, median, minimum, and maximum). Qualitative variables (e.g., sex and race) will

be summarized with counts and percentages.

The demographic parameters will include age, gender race height, weight and body mass index. Age will also be presented as a categorical variable (18-29 years, 30-49 years, 50-64 years and >=65 years). The baseline characteristics include:

- Asthma history and baseline disease characteristics which includes smoking history (never, current and former), age at onset (years) asthama diagnosis, time since diagnosis, asthma duration categories (1 to <5 years, 5 to <10 years, 10 to <15 years, 15 to <20 years, 20 to <25 years and >=25 years), experienced exacerbations in the previous 12 months, optimized OCS dose, duration of OCS dose prior to screening. Baseline optimized OCS dose also presented as a categorical variable (<7.5 mg/day, 7.5 to <15 mg/day, 15 to <30 mg/day and >=30 mg/day).
- Asthma exacerbations history which includes number of exacerbations (both descriptive and categorical), exacerbation types and causes of exacerbations in the previous 12 months.
- Family history of cardiovascular risk factors
- Past and current medical conditions
- Lung function test results at screening and baseline which includes pre- and post-bronchodilator FEV₁ (L), pre-bronchodilator percent predicted FEV₁ (%), pre-bronchodilator forced vital capacity (FVC) (L), reversibility (in mL and in %) and pre-bronchodilator FEV1/FVC.

By-subject listings of demographic and baseline characteristics will be provided for the safety populations.

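### SAP 7.2.2 sets baseline at the screening visit, contrary to the protocol and the rest of the SAP, and its eDiary baseline does not match SAP Appendix 3

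*SAP*

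**What the plan says.** SAP 7.2.2 opens with the general rule: "Baseline is defined as the value recorded at Visit 1 pre-dose assessment". For variables collected on the eDiary device, "the baseline is defined as the average of 4-weekly data collected in the run-in period". The next paragraph turns to Visit 2. A recorded assessment time decides whether a value is pre-dose; where there is none, "it will be assumed that all assessments on Visit 2 occurred prior to the administration of the study drug".

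Other places say something different:

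- Protocol 1.3 (Schedule of Activities): "Visit 2 (Week 0) will be considered Baseline".
- SAP 7.2.6: the exacerbation assessment period is "calculated from date of Baseline (Week 0) visit to date of Week 24 visit or early withdrawal".
- SAP 9.2 summarises "Lung function test results at screening and baseline which includes pre- and post-bronchodilator" FEV1, so it treats screening and baseline as separate time points.
- SAP Appendix 3: the baseline window for daily eDiary variables runs from seven days before Visit 2 to the day of first dose. For ACQ-5 the window is study day -7 to day 1, and the score nearest day 1 is taken.

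On precedence, SAP section 2 says that "any differences described here supersede the analysis presented in the protocol".

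**The concern.** No drug is given at Visit 1, so calling a Visit 1 value pre-dose distinguishes nothing. The phrase makes sense only at the dosing visit, Visit 2. As it stands, the section that defines baseline for every change score names a different visit from the protocol and from the SAP's own exacerbation section.

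This is a single-arm study, so baseline is the only comparator for a change score. Four of the seven secondary endpoints are of that kind: pre-bronchodilator FEV1, post-bronchodilator FEV1, ACQ-5 and morning PEF. If 7.2.2 and the other sections can each be followed in good faith, two programmers could produce different results for these endpoints under one SAP.

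**Working it through.** The plan gives no figure on this point to reproduce. The check compares the texts and counts days.

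**1. Timing.** Protocol 1.1 and 4.1.1 put screening 1 to 2 weeks before the first dose, which is at Visit 2. The run-in is therefore 7 to 14 days. From a Visit 1 baseline, the nominal Week 24 change spans 24 + 1 = 25 to 24 + 2 = 26 weeks.

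**2. Which visit is baseline?**

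| Source | Baseline |
|---|---|
| SAP 7.2.2, first sentence | Visit 1 |
| SAP 7.2.2, second paragraph | Implies Visit 2: its pre-dose rule has no use otherwise |
| SAP 7.2.6 | Week 0 (Visit 2) |
| SAP 9.2 | Distinct from screening; no visit named |
| Protocol 1.3 | Visit 2 (Week 0) |

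The 9.2 wording is the weakest of these. The Schedule of Activities, 7.2.6 and the Visit 2 rule carry the point. The precedence clause ranks the SAP over the protocol but cannot settle a conflict between two parts of the SAP.

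**3. Effect of the first sentence if followed literally, using the Schedule of Activities.**

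- Pre-bronchodilator FEV1, haematology, chemistry, vital signs and ECG are collected at both visits, so the screening value replaces the Week 0 value. This includes the blood eosinophil ratio to baseline in SAP 10.4.
- Post-bronchodilator FEV1 is marked at both visits, but the schedule note and Protocol 8.1.3 describe the Visit 2 procedure as an optional repeat. The choice matters only where a Visit 2 value exists.
- WPAI-GH is first collected at Visit 2. The change from baseline planned in SAP 4 and 10.3.2 could not be computed.

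**4. eDiary variables.** A 4-weekly average implies 4 × 7 = 28 days. The current run-in supplies 7/28 = 25% to 14/28 = 50% of them. Even if the ±7-day treatment-visit window is assumed to apply to Visit 2, the maximum is 14 + 7 = 21 days, still short of 28. The Appendix 3 daily window is 7 + 1 = 8 days, and its ACQ-5 baseline is a single score rather than an average. Section 7.2.2 does not refer to Appendix 3.

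**5. The data minimum.** Appendix 3 requires at least 7 days of data in a 4-weekly period. Protocol 5.3 admits participants with 4 of the last 7 diary days. Adding the dosing day gives 4 + 1 = 5, which is below 7. If the minimum were applied to the baseline row, an eligible participant could have no PEF baseline.

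**6. Count.** Of the seven secondary endpoints, two (pre- and post-bronchodilator FEV1) meet the Visit 1 conflict and two (ACQ-5, morning PEF) meet the eDiary conflict. The other three are exacerbation counts, which do not use this definition.

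**The case against.** The strongest reply is that this is one mistaken sentence whose meaning is plain from its surroundings, and that it would be caught. Much of that stands. SAP 9.2 and Table 14.1.2.8 in SAP Appendix 5 report screening and baseline lung function separately, so a Visit 1 baseline would show up as duplicated results. Missing WPAI-GH baselines would be noticed at once. A reader might infer that the wrong FEV1 baseline would pass unseen; the documents do not support that.

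The eDiary conflict is also softer than it first appears. Appendix 3 introduces its windows as the means of deriving 4-weekly averages and includes a baseline row, so 4-weekly may simply be the SAP's name for that derivation.

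Other stronger readings also go too far:

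- *No participant could have 28 run-in days.* Participants treated before Amendment 4 had an optimisation phase of a length the documents do not give. The day count holds only for the current schedule.
- *Three visits are labelled baseline.* Protocol Appendix 6 does say "Monitor participants weekly until liver chemistries resolve, stabilize or return to within baseline i.e. Visit 3". That concerns liver monitoring, not the analysis baseline. It should be reconciled with the Schedule of Activities as a separate matter.
- *Body weight loses its baseline.* Weight is measured at Visit 1 whether it belongs to the physical examination or to vital signs.
- *Pre-dose antibody samples would count as post-baseline.* This is speculative, because the Visit 2 rule treats untimed assessments at that visit as pre-dose.
- *FEV1 improvement would be inflated.* Entry requires FEV1 below 80% predicted at Visit 1 or Visit 2, so either reading may be the qualifying one. Neither the direction nor the size of any shift can be derived.

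What remains is that likely detection does not replace a correct definition. The general rule contradicts other parts of the SAP, and the eDiary sentence gives no route to Appendix 3.

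**Conclusion.** SAP 7.2.2 is wrong as written and should be fixed. Its general rule names the screening visit, against the protocol, SAP 7.2.6 and its own second paragraph. Its eDiary rule cannot be carried out as a 28-day average for participants on the current 7 to 14 day run-in, and it differs from Appendix 3, which is probably the intended rule.

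The reach is limited to secondary, exploratory and descriptive results. It includes the four change-from-baseline secondary endpoints, split two and two between the conflicts. The primary adverse event endpoint, exacerbation counts, OCS dose (defined separately in SAP 7.2.5) and sample size are not affected. Nasal polyps are not affected either, because Visit 1 is their only pre-treatment assessment. No formal hypothesis is tested.

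The conclusion rests on the visit schedule as printed. That the sentence is a drafting slip is an inference. The numerical effect on FEV1, ACQ-5 or PEF cannot be calculated from the documents.

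**What to change.** Replace the first paragraph of SAP 7.2.2 with:

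> Baseline is the last non-missing value before the first dose of mepolizumab, normally Visit 2 (Week 0); Visit 1 is used where Visit 2 is not scheduled or is missing. For eDiary variables, baseline is the Appendix 3 baseline window.

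In addition:

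- Delete the 4-weekly run-in average.
- Keep the Visit 2 timing rule, which then has a purpose.
- Leave OCS dose to SAP 7.2.5.
- State in Appendix 3 that the 7-day data minimum applies to post-baseline 4-week periods only.

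The cost is SAP wording and dataset derivations, with no new assessments. The drawback is that post-bronchodilator FEV1 baselines may come from different visits in different participants, so the source visit should be flagged in the dataset. An extra sensitivity analysis on this would be a matter of preference; the correction does not need it.
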